5.2.1 COVID-19 impact analysis

The World Health Organization (WHO) declared the novel COVID-19 outbreak a global pandemic on 11 Mar 2020. For the purposes of summarizing disposition with respect to COVID, post-COVID refers to an event or record reported after the date when WHO declares the global pandemic has ended. If the WHO has not declared an official end date by the end of the study, an alternative end date may be used at the discretion of study team.

If no suitable end date exists, the global pandemic will be considered ongoing, and the summaries by during and post-pandemic period described below will not be produced.

To assess the impact of the COVID-19 pandemic on the study, the following summaries will be presented (if there is a suitable pandemic end date):

12tion

- A summary of study participant disposition based on enrollment during and post COVID-19 pandemic
- A summary of study participant demographics based on enrollment during and post COVID-19

Treatment emergent AE data will also be analyzed during and post COVID-19 pandemic if applicable, details can be found in 5.6.2.2.

The following summary will also be provided:

• A summary of study visits impacted, and type of impact by the COVID-19 pandemic

5.3 **Primary Endpoints Analysis**

The co-primary efficacy variables for this study are PASI90 response and IGA 0/1 response at Week 16 and the corresponding analyses are based on the RS.

5.3.1 Definition of endpoints

5.3.1.1 PASI90 at Week 16

PASI90 is defined to be equal to 1 if the percentage improvement from Baseline in the PASI scores is 90% or greater and 0 if the percentage improvement from Baseline is less than 90%. This definition is introduced for the purpose of identifying study participants who respond to the treatment

(1 = responder, 0 = non-responder).

 $Percent\ Improvement\ from\ Baseline\ =\ 100\times \frac{Baseline\ PASI\ -\ Post\ Baseline\ Timepoint\ PASI}{Baseline\ PASI\ }$

The PASI is the most commonly used and validated assessment for grading the severity of PSO in clinical studies (Feldman, 2004). The PASI quantifies the severity and extent of the disease and weighs these with the percentage of BSA involvement. The PASI will be completed by the Investigator electronically at the visits specified in the protocol schedule of assessment.

The percent area of involvement (BSA%) is estimated across 4 body areas: head, upper extremities, trunk, and lower extremities. Assessors will enter the degree of involvement for a given region on a scale of 0 to 6 (0=none; 1=1% to <10% affected; 2=10% to <30% affected; 3=30% to <50% affected; 4=50% to <70% affected; 5=70% to <90% affected; 6=90% to 100% affected). This degree score is used in the calculation of PASI score as shown in Table 2. The total percent body surface area (BSA) of PSO involvement will also be estimated as a number between 0 and 100.

The Investigator assesses the average redness, thickness, and scaliness of lesions in each body area (each on a 5-point scale); 0=none, 1=slight, 2=moderate, 3=marked, and 4=very marked. The PASI score ranges from 0 to 72, with a higher score indicating increased disease severity. Detailed information of PASI scores could be found in 6.1.5.1.

			Degree of involvement of body
Body area	Details of area	BSA	area ^a
Head	Face, back of head	10%	0 to 6
Upper extremities	Left, right, upper, lower, flexor surface, extensor surface	20%	0 to 6
Trunk	Front, back, groin	30%	0 to 6
Lower extremities	Left, right, upper, lower, flexor surface, extensor surface, including buttocks	40%	0 to 6
Total		100%	

Table 2: Body areas for calculation of percent BSA for PASI

BSA=body surface area; PASI=Psoriasis Area and Severity Index

^a Where 0=none; 1=1% to <10% affected; 2=10% to <30% affected; 3=30% to <50% affected; 4=50% to <70% affected; 5=70% to <90% affected; 6=90% to 100% affected

5.3.1.2 IGA 0/1 (clear or almost clear with at least a 2-category improvement from Baseline) at Week 16

IGA 0/1 response is defined as clear [0] or almost clear [1] with at least a 2-category improvement from Baseline at Week 16.

A static IGA for PSO will be used to assess disease severity in all study participants during the study. The IGA will be completed at the visits specified in the protocol schedule of assessments.

The Investigator will assess the overall severity of PSO using the following 5-point scale presented in Table 3 below.

Table 3: Five-point IGA

	Score	Short descriptor	Detailed descriptor
	0	Clear	No signs of PSO; postinflammatory hyperpigmentation may be present
	1	Almost clear	No thickening; normal to pink coloration; no to minimal focal scaling
	2 mellin	Mild	Just detectable to mild thickening; pink to light red coloration; predominately fine scaling
5	300 36	Moderate	Clearly distinguishable to moderate thickening; dull to bright red, moderate scaling
	4	Severe	Severe thickening with hard edges; bright to deep dark red coloration; severe/coarse scaling covering almost all or all lesions

IGA=Investigator's Global Assessment; PSO=psoriasis

ation

5.3.2 Main analytical approach

The primary estimand for the co-primary endpoints is defined as follows:

- Treatment: Bimekizumab 320mg Q4W for 16 weeks
- Target Population: adult Korean study participants meeting the protocol-specified inclusion/exclusion criteria
- Intercurrent event handling:

An intercurrent event is defined as discontinuation of IMP prior to Week 16. A composite strategy will be implemented in which a positive clinical outcome is defined as achieving PASI90/IGA 0/1 response at Week 16 and not discontinuing IMP through Week 16. Study participants with intercurrent event of discontinuation of IMP prior to Week 16 will be considered nonresponders (i.e. negative clinical outcome).

• Population level summary: odds ratio comparing bimekizumab to placebo

In the above scenario, missing data at Week 16 that are not preceded by an intercurrent event, as well as any data after an intercurrent event, will be imputed as non-responders. While this approach is described as a composite strategy for intercurrent event handling, it is equivalent to applying non-responder imputation (NRI).

The primary analysis of the co-primary endpoints will be based on the Cochran-Mantel-Haenszel (CMH) test. The evaluation of superiority to placebo will use treatment comparisons based on the CMH test using the p-value for the general association. The odds ratio and associated confidence interval (CI) based on the Wald test will be presented. If one of the treatment groups has 0 or very low response where CMH is no longer an appropriate method, Fisher's exact test will be applied and the odds ratio will not be calculated.

The number and percentage of study participants who are PASI90 responders at Week 16 will be summarized. IGA 0/1 response will be summarized in the same manner as the PASI90 responder variable.

A line plot of the PASI90 and IGA 0/1 responder rate over time by treatment group will be produced.

By-study participant listings of PASI and IGA responder variables, PASI and IGA data will be provided.

PSD (P-SIM) response for itch, pain and scaling at Week 16 5.4.1.1.4

The PSD (P-SIM) consists of 14 items, measuring the following PSO-related signs, symptoms, and functional impacts: redness, scaling, cracking, lesions, thickening, itch, pain, burning, dryness, irritation, sensitivity, fatigue, embarrassment, and choice of clothing. Each item is assessed for severity/impact level over a recall period of the past 24 hours on a 0 to10 scale, where 0 means no symptoms or impact and 10 means very severe symptoms or worst impact.

Weekly averages will be derived for each of the items of the PSD for weeks matching the post-Baseline dosing weeks up to Week 16. A weekly average is the sum of the scored item over the course of the study week divided by the number of days on which the item was completed. The weekly averages will be relative to the respective visit date except for Baseline, which will be

anchored to the first dose of study drug. A weekly average will only be calculated if at least 4 non-missing values (not necessarily consecutive) are available. Otherwise, the PSD weekly average for the given question will be set to missing.

Baseline will be computed as the average from the last 7 consecutive day period prior to the Baseline visit in which there are at least 4 non-missing entries. That is, to start, we consider the last 7 consecutive days prior to the Baseline visit, but not including the Baseline visit day itself. If there are at least 4 non-missing values (not necessarily consecutive), then the Baseline average will be calculated. If there are less than 4 values, the 7 consecutive day period will move one day earlier. If there are at least 4 non-missing values (not necessarily consecutive) in that period, then the Baseline average will be calculated. This will continue until there are at least 4 non-missing values in a 7 consecutive day period in the 14 days prior to Baseline. If there is no period in which there are at least 4 non-missing entries, then the Baseline value will be set to missing.

If more than one set of PSD scores are submitted on a particular date, only the record where the submission date matches the expected PSD entry date will be used in the calculation of weekly scores.

Each of three PSD response scores -itch, pain, and scaling- will be characterized in terms of the cumulative percent of study participants demonstrating a pre-specified point improvement at Week 16. The thresholds for the PSD response score of itch, pain, and scaling are 4.00. For this responder analysis, it will be limited to the study participants with a Baseline PSD response score at or above the applicable threshold score (4.00).

PSD compliance rate and completion rate at Baseline and Week 16 for each of the 3 items (Pain, Itch, and Scaling) will be derived as follows:

Compliance rate: the percentage of study participants in the RS with a non-missing weekly item score at each visit.

Completion rate: the percentage of study participants who have completed a particular visit with a non-missing weekly item score.

5.4.1.1.5 Scalp IGA 0/1 at Week 16

A static IGA for scalp PSO will be used to assess disease severity on the scalp.

The scalp IGA will be assessed for all study participants at Baseline. The scalp IGA will be completed by the Investigator electronically. Only study participants with a scalp IGA score >0 at Baseline will have the scalp IGA assessed at later visits as specified in the protocol schedule of assessments.

Scalp lesions will be assessed in terms of clinical signs of redness, thickness, and scaliness using a 5-point scale (Table 4).

Table 4: Scalp IGA

(his	Score	Short descriptor	Detailed descriptor
*	0	Clear	Scalp has no signs of PSO; postinflammatory hyperpigmentation may be present

Bimekizumab

1	Almost clear	Scalp has no thickening; normal to pink coloration; no to minimal focal scaling
2	Mild	Scalp has just detectable to mild thickening; pink to light red coloration; predominately fine scaling
3	Moderate	Scalp has clearly distinguishable to moderate thickening; dull to bright red, moderate scaling
4	Severe	Scalp has severe thickening with hard edges; bright to deep dark red coloration; severe/coarse scaling covering almost all or all lesions

PSO=psoriasis

The binary response variable Scalp IGA response at Week 16 is defined as clear [0] or almost clear [1] with at least a 2-category improvement from Baseline to Week 16. For analysis purposes, the evaluation of scalp IGA response will be limited to study participants with a Baseline scalp IGA of at least 2. Therefore, if a study participant has a score of 2 at Baseline, they can only be considered a responder if their IGA is 0 (thereby meeting the criterion for a 2-category improvement from Baseline). Study participants with a Baseline scalp IGA of 1 will be assessed per the protocol but will not be part of the scalp IGA analysis.

5.4.1.1.6 DLQI 0/1 response at Week 16

The DLQI questionnaire is used for patients with psoriasis and consists of 10 questions. This is a validated, quality-of-life questionnaire that covers 6 domains including symptoms and feelings, daily activities, leisure, work and school, personal relationships, and treatment, as assessed over the past week.

The scoring of each answer for the DLQI is as follows:

Table 5: Dermatology Life Quality Index

DLQI Scoring			
Response	Score		
Very much	3		
Alot	2		
A little	1		
Not at all	0		
Not relevant	0		

Question unanswered	0
Q7: "prevented work or studying" = yes	3

naiketing authorizati naiketing authorizati adin. The DLQI total score is calculated by adding the score of each question. The maximum score is 30, and the minimum score is 0. The higher the score, the more quality of life is impaired.

Meaning of DLQI Scores:

0-1 = no effect at all on patient's life

2-5 = small effect on patient's life

6-10 = moderate effect on patient's life

11-20 = very large effect on patient's life

21-30 = extremely large effect on patient's life

This categorization will not be utilized in the analysis.

Because Q7 has a sub-question (referred to as Q7a here) after the leading yes/no question, some clarifying rules for scoring are provided:

- If Q7 is marked as "yes", a score of 3 is given regardless of the responses to Q7a. •
- If Q7 is marked as "no", "not relevant", or is missing and Q7a is "A lot", a score of 2 is given.
- If Q7 is marked as "no", "not relevant", or is missing and Q7a is "A little", a score of 1 is given.
- If Q7 is marked as "no", "not relevant", or is missing and Q7a is "Not at all", a score of 0 is given.
- If Q7 is marked as "no" or "not relevant" and Q7a is missing, a score of 0 is given.
- If Q7 is missing and Q7a is missing, Q7 is considered unanswered (see below for details on • how this impacts the overall DLQI score).

If 1 question is left unanswered, this is scored 0 and the scores are summed and expressed as usual out of a maximum of 30. If 2 or more questions are left unanswered, the questionnaire is not scored.

A DLQI total score of 0 or 1 indicates no impact of the disease on patient's life.

The binary response variable DLQI 0/1 response (defined as a DLQI total score of 0 or 1) at Week 16 will be evaluated as a secondary endpoint.

5.4.1.1.7 Percentage of Body Surface Area (BSA) affected by PSO at Week 16

The percentage BSA affected by PSO is recorded as a number between 0 and 100 recorded at visits where skin is assessed.

The percent change from baseline in BSA is defined as:

Post Baseline BSA – Baseline BSA Percent change from Baseline = $100 \times -$ **Baseline BSA**

5.4.1.2 Main analytical approach

5.4.1.2.1 **Binary endpoints**

The binary secondary efficacy endpoints include:

- PASI100 response at Week 16,
- IGA 0 response at Week 16,
- PASI75 response at Week 4,
- PSD [P-SIM] [itch, pain, and scaling] response at Week 16,
- Scalp IGA 0/1 response at Week 16,
- DLOI 0/1 response at Week 16

o authorization Viereot These secondary endpoints will have the same estimand structure as for the co-primary endpoints, which is defined as follows:

- Treatment: Bimekizumab 320mg Q4W for 16 weeks
- Target Population: adult Korean study participants meeting the protocol-specified inclusion/exclusion criteria
- Intercurrent event handling: •
 - PASI100 response at Week 16, IGA 0 response at Week 16, PSD [P-SIM] [itch, pain, and scaling] response at Week 16, Scalp IGA0/1 response at Week 16, DLQI 0/1 response at Week 16

An intercurrent event is defined as discontinuation of IMP prior to Week 16. A composite strategy will be implemented in which a positive clinical outcome is defined as achieving response at Week 16 and not discontinuing IMP through Week 16. Study participants with intercurrent event of discontinuation of IMP prior to Week 16 will be considered nonresponders (i.e. negative clinical outcome).

PASI75 response at Week 4

An intercurrent event is defined as discontinuation of IMP prior to Week 4. A composite strategy will be implemented in which a positive clinical outcome is defined as achieving response at Week 4 and not discontinuing IMP through Week 4. Study participants with intercurrent event of discontinuation of IMP prior to Week 4 will be considered nonresponders (i.e. negative clinical outcome).

Population level summary: odds ratio comparing bimekizumab to placebo

In the above scenario, missing data at the time point of interest that are not preceded by an intercurrent event, as well as any data after an intercurrent event, will be imputed as non-responders. While this approach is described as a composite strategy for intercurrent event handling, it is equivalent to applying non-responder imputation (NRI).

The number and percentages of PASI100, IGA 0, PSD [itch, pain, and scaling] responders, Scalp IGA, DLQI 0/1 responders at Week 16 and PASI75 responder at Week 4 will be reported for each treatment group.

The evaluation of superiority to placebo will use treatment comparisons based on the CMH test using the nominal p-value for the general association. The odds ratio and associated confidence interval (CI) based on the Wald test will be presented. If one of the treatment groups has 0 or stil2ation very low response where CMH is no longer an appropriate method, Fisher's exact test will be applied and the odds ratio will not be calculated.

A line plot of the responder rate over time by treatment group will be produced.

By-study participant listings of the secondary efficacy binary variables will be provided.

5.4.1.2.2 **Continuous endpoint**

The continuous secondary efficacy endpoint is the percent change from Baseline in BSA affected by PSO at Week 16.

The estimand to define the treatment effect of interest for the continuous secondary efficacy endpoint is as follows:

- Treatment: 320mg bimekizumab Q4W for 16 weeks. •
- Target Population: adult Korean study participants meeting the protocol-specified ٠ inclusion/exclusion criteria.
- Intercurrent event handling: A hypothetical strategy will be implemented in which the • estimand targets the treatment difference in a scenario where an intercurrent event does not occur, such that outcomes for study participants without an intercurrent event are as observed, and outcomes for study participants with an intercurrent event are treated as though they had completed the randomized study treatment through Week 16 by imputing data following an intercurrent event using LOCF.
- Study participant-level summary measure: Difference in the adjusted means between bimekizumab and placebo.

For the continuous change from Baseline efficacy endpoint, percent change from Baseline in BSA affected by PSO at Week 16, an analysis of covariance (ANCOVA) model will be used with fixed effects of treatment and Baseline value as a covariate. Missing data will be imputed via LOCF.

Sensitivity analysis 5.4.1.3

For all secondary efficacy endpoints, sensitivity analysis based on observed cases will be performed. Study participants with missing data or who have prematurely discontinued IMP will be treated as missing. The same analysis method applied for the primary endpoints will be used for binary endpoints and ANCOVA model for continuous endpoint as in the secondary efficacy analysis will be used.

An additional sensitivity analysis will be performed on DLQI 0/1 at Week 16 which will exclude study participants with a missing Baseline DLQI score. Missing baseline DLQI scores can be due to study participants not completing an assessment until after the first dosing visit or due to late entry of the intended Baseline scores. The scores should be entered directly into the database by the study participant at the Baseline visit, however due to some technical problems for a few subjects this was not possible, and the scores were collected on paper and entered at a later date.

orization

As only the date that the scores were entered electronically is captured in the database, these records are considered post-baseline for the purpose of analysis.

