9.8 Determination of sample size

Sample size and power calculations are performed based on a total of 45 study participants being randomly assigned in a 2:1 ratio at Baseline to one of the following treatment groups:

- Bimekizumab 320mg Q4W (30 study participants)
- Placebo (15 study participants)

The primary efficacy analysis is based on the comparison of bimekizumab to placebo for the co-primary efficacy endpoints of PASI90 and IGA 0/1 response at Week 16. The assumed responder rates for PASI90 at Week 16 are 70% and 13.3% for bimekizumab and placebo, respectively. Based on the number of study participants planned, this equates to 21 and 2 responders in the bimekizumab and placebo treatment groups, respectively. In the global Phase 3 bimekizumab PSO program, the PASI90 responder rate ranged from 85% to 90%. The assumption here is relatively low to account for increased variability due to a small sample size and the possibility of missing data due to COVID-19. Additionally, the placebo PASI90 responder rate assumption is higher than observed in the Phase 3 program to account for potential variability due to small sample size. These assumptions are conservative against a bimekizumab treatment effect.

The power to show statistical superiority of bimekizumab relative to placebo at a 2-sided significance level of 0.05 under these assumptions is 95% for PASI90 at Week 16. As the Phase 3 studies demonstrated similar responder rates between PASI90 and IGA 0/1, this calculation is considered sufficient to justify the sample size. These calculations were performed using nQuery Advisor[®] 7.0 based on a two-group continuity corrected chi-square test of equal proportions (with unequal n).

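### The BSA percent-change ANCOVA pools one residual variance over a 2:1 split; if the 15-person placebo arm varies more, as is likely but not certain, the standard error is too small

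*SAP*

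**What the plan says.** - **Model.** SAP 5.4.1.2.2, and protocol 9.3.3 in the same words: "an analysis of covariance (ANCOVA) model will be used with fixed effects of treatment and Baseline value as a covariate". Neither describes a residual variance structure, a robust standard error, an unequal-variance test or a rank-based check.
- **Summary measure.** "Difference in the adjusted means between bimekizumab and placebo" (SAP 5.4.1.2.2). No confidence interval is named for it. The interval in SAP 5.4.1.2.1 belongs to the odds ratios of the binary endpoints.
- **Sensitivity.** SAP 5.4.1.3 repeats the same ANCOVA on observed cases, and SAP 5.4.1.4 rules out supplementary analyses. The binary endpoints have Fisher's exact test as a fallback. The continuous endpoint has no fallback.
- **Design.** "a total of 45 study participants being randomly assigned in a 2:1 ratio at Baseline to one of the following treatment groups" (protocol 9.8): 30 bimekizumab, 15 placebo.
- **Expected response.** In the global programme "the PASI90 responder rate ranged from 85% to 90" per cent. For planning, "The assumed responder rates for PASI90 at Week 16 are 70% and 13.3% for bimekizumab and placebo, respectively".
- **Scale.** "The percentage BSA affected by PSO is recorded as a number between 0 and 100" (SAP 5.4.1.1.7), and the endpoint is percent change from Baseline in that number.
- **Status.** Secondary endpoints get nominal p-values only (SAP 5.4), and values below 0.001 all print as <0.001 (SAP 5.1).

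**The concern.** BSA cannot go below zero, so percent change stops at -100%. If most bimekizumab participants clear or nearly clear, their values pile up at that floor with little spread. Placebo values can move either way, and the ceiling is remote: from the eligibility minimum of 10% BSA it is 100 × (100 - 10)/10 = +900%.

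A pooled residual variance is weighted mainly by the larger arm. The sampling variance of the difference depends mainly on the smaller arm. With 2:1 allocation, a more variable placebo arm therefore makes the standard error too small, and more data at the same ratio would not cure it.

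This is a bridging study and the endpoint is not formally tested. Its value lies in the size of the adjusted difference and the error bars around it, and the error bars are what would be wrong.

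**Working it through.** **The plan's own figure.** The only power figure is for PASI90, not BSA: "The power to show statistical superiority of bimekizumab relative to placebo at a 2-sided significance level of 0.05 under these assumptions is 95" per cent, from a "two-group continuity corrected chi-square test of equal proportions". I reproduced it only to confirm the arm sizes and rates. With 15 placebo, ratio 2 and difference 0.70 - 0.133 = 0.567, the effective uncorrected placebo size is (15 - 3/(4 × 0.567))²/15 = 12.47. Then z = (0.567 × √12.47 - 1.96 × √(1.5 × 0.511 × 0.489)) / √(0.133 × 0.867 + 0.70 × 0.30/2) = 1.71, which gives 95.6% power. The figure holds. No figure for BSA exists to reproduce.

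**Inputs.** n = 30 and 15 (protocol 9.8). The SDs of BSA percent change are not in either document, so those below are assumptions (percentage points, s₁ bimekizumab, s₂ placebo).

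**Formulas**, leaving out the covariate:
- Pooled SE = √[ ((29s₁² + 14s₂²)/43) × (1/30 + 1/15) ]
- True SE = √( s₁²/30 + s₂²/15 )

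Example at 20/30: pooled = √(24,200/43 × 0.1) = √56.28 = 7.50; true = √(13.33 + 60) = 8.56; ratio 0.88.

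Coverage is from simulated trials of this design (8,000 to 20,000 per SD pair), fitting the ANCOVA with its Baseline covariate.

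| s₁/s₂ | SD ratio | Pooled SE | True SE | Pooled/true | Coverage of nominal 95% CI |
|---|---|---|---|---|---|
| 20/20 | 1 | 6.32 | 6.32 | 1.00 | 95.0% |
| 20/25 | 1.25 | 6.88 | 7.42 | 0.93 | 93.2% |
| 20/30 | 1.5 | 7.50 | 8.56 | 0.88 | 91-92% |
| 20/40 | 2 | 8.89 | 10.95 | 0.81 | 88.8% |
| 10/30 | 3 | 6.00 | 7.96 | 0.75 | 85% |
| 20/10 | 0.5 | 5.50 | 4.47 | 1.23 | not simulated |

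At 30/20, with bimekizumab the more variable arm, coverage was 97.5%, so the interval is too wide. HC3 and Welch intervals stayed at about 94-96% in every case tried. A skewed case with the active arm bounded at the floor (SD 18 against 35) gave 88.6% for the pooled analysis and 95.2% for both HC3 and Welch.

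**Interval width.** At 20/40 the half-width is 17.9 points pooled and 23.1 with unequal variances; at 10/30 it is 12.1 and 16.9.

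**Which SD ratio is plausible?** A rough proxy treats PASI90 responders as having mean change -97 (SD 4), active nonresponders -60 (SD 20) or -50 (SD 30), and placebo nonresponders -5 (SD 20 to 40). All of these are assumptions. At 85% active response with nonresponders at -60, s₁² = 0.85 × 16 + 0.15 × 400 + 0.85 × 0.15 × 37² = 248, so s₁ = 15.8. With no placebo responders and placebo SD 30, the ratio is 1.9 and the SE ratio 0.82. Over the grid:
- Active 85-90%, placebo 0 to 13.3%: SD ratio about 1.3 to 3.7, SE ratio 0.92 to 0.74.
- Active 70%, placebo 0 to 13.3%: SD ratio about 1.0 to 2.4, SE ratio 1.01 to 0.78.

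**p-value.** Across this grid the mean differences were 66 to 88 points, and every pooled and Welch p-value was below 0.0001. All would print as <0.001.

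**The case against.** The best case for leaving the plan alone has five parts.

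1. **No SD is given, and the active-arm rate is open to choice.** This stands. A reader might infer that placebo will certainly vary much more. The documents do not say so, and at 70% active response with few placebo responders the ratio can be near 1. Pairing the 85-90% Phase 3 rate with the 13.3% placebo planning rate is also a mismatch, since protocol 9.8 says 13.3% is above what was seen. Dropping that pairing changes little: with 0 or 2% placebo responders (assumed) the ratio is still about 1.3 to 3.1. The plan's own pair, 70% and 13.3%, gives about 1.5 to 2.4.
2. **LOCF can widen the active arm.** This also stands. One early dropout among 30, carried forward near 0 while the others average -95 (assumed), adds 95 × √((1/30)(29/30)) = 17 points of SD. An SD of 10 becomes about 20, and the 10/30 case moves to a ratio of about 1.5.
3. **No CI is specified for this endpoint.** Correct. The coverage figures apply only if one is reported; the standard error is affected either way.
4. **The p-value and the conclusions are untouched.** Correct. A reader might infer that the nominal p-value misleads. If there were no effect at all, both arms would share one distribution and the pooled p-value would be valid. At the expected effect both methods print the same value. Superiority rests on PASI90 and IGA 0/1 alone (SAP 2).
5. **Unequal spread will be visible.** Partly. SAP 5.5.2 plans by-arm summaries of BSA change, with SDs under SAP 5.1. They use observed data without Baseline adjustment, so an interval rebuilt from them would not match the LOCF ANCOVA.

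**Conclusion.** The concern holds as a limited point about precision. The plan pools one variance over 30 and 15 participants and offers no alternative. The floor at -100% and the Phase 3 response rate make a more variable placebo arm likely, not certain. Under assumed SD ratios of 1.25 to 3, the standard error is about 7% to 25% too small. A ratio of 1 gives no error, and a ratio below 1 reverses its direction.

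The documents do not support a stronger reading. The adjusted mean difference is not biased by unequal variances. The superiority conclusion and the printed nominal p-value are not expected to move. The change is still worth making, because it costs almost nothing and gives sound error bars whichever arm varies more.

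**What to change.** In SAP 5.4.1.2.2, keep treatment and Baseline value as the model terms and add a residual variance estimated separately by treatment, with Satterthwaite or Kenward-Roger degrees of freedom (in SAS, PROC MIXED with REPEATED and GROUP=treatment). HC3 standard errors are an acceptable alternative. State that the 95% CI of the adjusted mean difference will be reported on that basis. Apply the same to the observed-case analysis in SAP 5.4.1.3, and record the choice in SAP 6.2 before unblinding, since adding it later would look post hoc.

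The cost is about one line of text and code; the estimand is unchanged. If the SDs prove equal, the approximate degrees of freedom fall from 42 to about 28 (for 20/20: 40²/(13.33²/29 + 26.67²/14) = 28.1). The t multiplier then rises from 2.02 to 2.05, an interval about 1.5% wider. If placebo is more variable, the interval is wider by more, as it should be.
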